### *Study Inclusion:*

Criteria for continuation into the long-term phase is based solely on proven clinical benefit using criteria universally accepted to be beneficial. The following criteria are accepted as evidence of substantial clinical benefit upon completion of CLINICAL PROTOCOL to investigate the efficacy of recombinant human leptin (METRELEPTIN) in nonalcoholic steatohepatitis (NASH) or nonalcoholic fatty liver disease (NAFLD) associated with lipodystrophy, MB002-014 (IRMBED: HUM00058708):

- Reduction of HbA1c  $\geq$ 1.0% or,
- Reduction of triglycerides  $\geq$ 30% of baseline or,
- Decrease in insulin requirements  $\geq$ 40% or,
- Reduction in total NASH score by  $\geq$ 2 points.
- Significant worsening of metabolic parameters after discontinuation of Metreleptin if discontinuation has been undertaken.

- A health condition that appears to have significantly improved by metreleptin for which two independent health care providers make a request to prevent drug discontinuation. In addition, the PI has to document absence of contraindications for drug continuation (such as bone marrow suppression).

*Study group:* We will enroll up to a total of up to 15 subjects to receive study drug Metreleptin from our parent studies.

*Restorative leptin therapy:* This is defined as administration of recombinant methionyl-human leptin subcutaneously to achieve high normal levels of circulating leptin in individuals who started out with lower than normal or low normal levels of circulating leptin(1, 2). Recombinant human leptin will be provided by Amryt Pharma (Boston, MA). Previous experience from patients with lipodystrophy or with congenital absence of leptin indicates that this goal can be achieved by administration of 0.02 to 0.10 mg/kg/day in adult males depending on baseline leptin concentrations and body surface area of the patients. In this study, patients will be treated with 2.5 and 5 mg /day (male and female respectively) to achieve high physiological concentrations. Higher dose titrations can be used in the judgment of the PI as indicated up to 10 mg daily. It is important to note that the patients enrolling in this long term study will be on metreleptin therapy that has been found effective, therefore, their dose will likely not change during this protocol. .

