*Treatment:* Up to fifteen patients will be enrolled into this long-term treatment extension study. Patients will be continued on metreleptin treatment as mentioned. This will be injected subcutaneously after reconstitution once a day in the morning at approximately the same time of the day that fits the subject's calendar. Dose may be titrated up to 15 mg daily based on metabolic response as needed.

*Follow-up schedule and monitoring:* Scheduled outpatient visits will occur at 6 month intervals. Tolerability will be assessed at each visit. During each visit, patients', weights, BMI, injection site inspection and basic laboratory data (comprehensive metabolic panel (fasting glucose, BUN, creatinine, sodium, potassium, chloride, CO2, calcium, total protein, albumin, total bilirubin, AST, ALT, alkaline phosphatase), fasting insulin, fasting leptin levels, fasting lipid panel (total cholesterol, triglycerides, HDL, LDL)), will be recorded. Throughout the study, lab work for CBC with differential count and creatinine kinase will be obtained at each visit.

Unscheduled visits may occur at more frequently than ever six months in order to follow-up on any adverse event or unanticipated health issues participants may be having.

*Study Termination:* Patient participation will be concluded five years after the patient's baseline appointment. At this time normal follow-up study procedures will be conducted, final drug accountability will be performed and patient will be transitioned to clinical care.

*Preparation for study visits:* Subjects will be asked to refrain from alcohol or tobacco use for 72 hours prior to the visit. They will report to the Research Center after 10 hours of fasting. They will be allowed to consume water overnight prior to the studies.

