**Amryt representative: [name]**

**Sr. Supply Chain Manager**

**Amryt Pharma PLC**

**[contact]**

### 3.3 DRUG DOSAGE AND ADMINISTRATION

Metreleptin will be administered by subcutaneous injection at the doses specified above. Subjects will be instructed by study personnel to reconstitute the medication and self-administer the injections and will perform the first injection under the supervision of study personnel.

The dosing recommendations for Metreleptin are listed below:

Body Weight	Gender	Daily Recommended Metreleptin Dose
≤40 kg	Male	0.06 mg/kg
	Female	
>40 kg	Male	2.5 mg (0.5 mL)
	Female	5.0 mg (1.0 mL)

Initial Metreleptin dose may be adjusted based upon the subject's dose at termination of the two previous studies for reasons of efficacy. Metreleptin dose may be adjusted at investigator's discretion based on clinical response (e.g. inadequate metabolic control or excessive weight loss or tolerability issues). Injections at a single site will have a maximum allowable volume of 2.0 ml. Preferably study medication will be administered at approximately the same time each day. Drug administration will occur once a day (QD). Metreleptin administration may be changed to twice a day (BID) at investigator's discretion based on clinical response (e.g. inadequate metabolic

control, tolerability issues). Dose exceeding 1.0 mL may be administered as two separate injections in order to minimize patient discomfort due to injection volume. Metreleptin dose can be injected into the abdomen, upper arm or thigh region depending on patient preference and comfort. The site(s) of injection will not occur on the limb from which subsequent blood draws will occur that day.

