## **6. WOMEN, MINORITY AND CHILDREN INCLUSION IN CLINICAL RESEARCH**

**1. Inclusion of Women:** The use of pregnant women is not the central focus of this research. Pregnancy, women who think they may be pregnant, women who are actively trying to conceive, and women who are currently breast-feeding are exclusion criteria for enrollment in this study. The general informed consent documents will advise sexual abstinence or use of contraception for female participants of child bearing age. The use of metreleptin is intended to provide direct benefit to women participating in this trial. There are no other accepted medical treatments that are likely to provide the same benefit.

**2. Inclusion of Minorities:** In our study, all patients with physician confirmed lipodystrophy and ultrasound confirmed non-alcoholic fatty liver disease will be recruited regardless of race and ethnicity. We will continue to do every effort to recruit minorities. If the number of minorities seems to be disproportionately low, we will ask for help from the MCRU Minority Recruitment Board.

**3. Inclusion of Children:** Subjects < 5 years old will not be included in this study as they would require a pediatric expertise not available at this study location. Subjects ≥ 5 years old will be included in this study as NAFLD in lipodystrophic patients is a rare disease with no other approved option for treatment. Liver biopsies are considered to be standard of care treatment for lipodystrophic patients and therefore these juvenile patients will not be placed at an unacceptable risk by having two liver biopsies performed as part of this research study. In this protocol's parent study and **in an ongoing study, FHA101, four pediatric patients have been successfully and safely treated with metreleptin.**

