## APPENDIX

Protocol Table 1: Schedule of Study Procedures			
Studies	Baseline	Follow up visits (occurring at six month intervals)	Unscheduled visit***
Fasting biochemistry	X	X	X
Fasting adipocytokines	X	X	X
Fasting appetite regulators	X	X	X
Leptin sampling	X	X	X
Metabolomics sample	X	X	X
HOMA-IR	X	X	X
Weight, Height, and Vitals	X	X	X
Study medication distribution and accountability	X	X	X
Leptin (mg/kg/day)	5.0 – 10.0 mg/day	5.0 – 10.0 mg/day	5.0 – 10.0 mg/day
***Study procedures may be omitted at investigator's discretion during unscheduled visits.

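### The protocol sets two different maximum daily doses (10 mg and 15 mg), and the 5.0 mg lower bound in Protocol Table 1 excludes the protocol's own doses for males and for patients of 40 kg or less

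*Protocol*

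**What the plan says.** The protocol states the metreleptin dose in four places.

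- **Study Inclusion (section 2.2), Restorative leptin therapy.** The planned doses are given by sex: "patients will be treated with 2.5 and 5 mg /day (male and female respectively"). The limit follows: "Higher dose titrations can be used in the judgment of the PI as indicated up to 10 mg daily". The paragraph adds that, because patients arrive on a dose that works, "their dose will likely not change during this protocol".
- **Study Inclusion (section 2.2), Treatment.** "Dose may be titrated up to 15 mg daily based on metabolic response as needed".
- **Section 3.3.** "Metreleptin will be administered by subcutaneous injection at the doses specified above". The dosing table that follows gives 0.06 mg/kg for either sex at 40 kg or less, 2.5 mg (0.5 mL) for males over 40 kg, and 5.0 mg (1.0 mL) for females over 40 kg. The text then allows changes: "Metreleptin dose may be adjusted at investigator's discretion based on clinical response". It gives no daily maximum.
- **Appendix, Protocol Table 1.** The row labelled "Leptin (mg/kg/day") shows 5.0 to 10.0 mg/day at baseline, at follow-up visits and at unscheduled visits.

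On age, section 6 states: "Subjects ≥ 5 years old will be included in this study".

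**The concern.** Both limits in section 2.2 govern titration of the same drug in the same patients during the same extension. Neither is described as a starting cap, a later cap or a cap for a subgroup, and neither comes from an amendment log. A patient on 12 mg is therefore compliant under the Treatment paragraph and over the limit under the Restorative leptin therapy paragraph and Table 1.

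The lower end of Table 1 raises a second conflict, which does not depend on titration. A male over 40 kg, or any patient of 40 kg or less, who receives the section 3.3 recommended dose is below the table's range at every visit.

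What is at stake is the reference against which dosing is judged. Section 5.7 asks for reports of overdose, underdose and medication errors. Section 5.10 makes every overdose an SAE but gives no numerical threshold. Section 4.4 lists noncompliance with protocol procedures among the reasons for removing a patient. With inconsistent limits, staff have no single figure for these judgments over up to five years of treatment per patient.

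**Working it through.** No sample-size or power formula is involved. The check compares the stated doses and does simple arithmetic on them.

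**Daily maximum, place by place**

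| Place | Daily maximum |
|---|---|
| Section 2.2, Restorative leptin therapy | 10 mg |
| Section 2.2, Treatment | 15 mg |
| Section 3.3 | none stated; points back to both |
| Appendix, Protocol Table 1 | 10.0 mg |

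- Difference: 15 − 10 = 5 mg. Ratio: 15 / 10 = 1.5.
- Relative to the recommended dose for males over 40 kg: 10 / 2.5 = 4 times against 15 / 2.5 = 6 times.
- Relative to the recommended dose for females over 40 kg: 10 / 5.0 = 2 times against 15 / 5.0 = 3 times.

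**Lower bound: Table 1 against the section 3.3 dosing table**

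| Group | Recommended daily dose | Within 5.0 to 10.0 mg? |
|---|---|---|
| 40 kg or less, either sex | 0.06 mg/kg, at most 0.06 × 40 = 2.4 mg | No |
| Male over 40 kg | 2.5 mg | No |
| Female over 40 kg | 5.0 mg | Yes, at the minimum |

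- Table 1 minimum over the male dose: 5.0 / 2.5 = 2.0.
- Table 1 minimum over the largest low-weight dose: 5.0 / 2.4 = 2.08. The ratio is larger at lower weights: the dose is 1.8 mg at 30 kg and 1.2 mg at 20 kg.

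Two of the three dosing groups therefore fall outside Table 1 at their recommended dose.

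**Does the handling information settle the maximum?**

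- Concentration from the section 3.3 table: 2.5 mg / 0.5 mL = 5 mg/mL.
- 10 mg: 10 / 5 = 2.0 mL, exactly the single-site limit in section 3.3, and 10 / 11.3 = 0.88 of a vial (vial content from section 3.4).
- 15 mg: 15 / 5 = 3.0 mL, so at least two sites, and 15 / 11.3 = 1.33 vials.

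These figures sit more naturally with 10 mg. They do not rule out 15 mg, because section 3.3 allows split injections and twice-daily dosing.

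**The case against.** The strongest reply concerns weight. The protocol expects doses to stay as they were at the end of the parent study, so the conflict over the maximum bites only if someone is titrated above 10 mg. Table 1 is a schedule of procedures, and a prescriber would use section 3.3, so its lower bound can be read as a badly filled appendix cell. Entry doses may also be set from the dose at the end of the previous studies, so a male or a light patient need not start on the section 3.3 recommendation. Enrolment is at most 15 patients, and the protocol does not show that any of them will weigh 40 kg or less.

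Much of this stands as a limit on practical impact. The lower-bound mismatch is the lesser of the two problems, and it arises only for patients actually on the recommended dose. The low-weight group is possible, given eligibility from age 5, but not shown to be present.

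None of it reconciles the two maxima. Setting Table 1 aside altogether leaves 10 mg and 15 mg in adjacent paragraphs. Sections 2.2 and 3.3 both provide for titration when metabolic response is inadequate, and discretion without a number cannot choose between two explicit numbers.

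**Conclusion.** The concern holds and should be fixed. The current text contains two incompatible daily maxima, 10 mg and 15 mg, and does not say which one applies. Table 1's 5.0 mg minimum also contradicts the protocol's own doses of 2.5 mg for males over 40 kg and at most 2.4 mg for patients of 40 kg or less. The mg/kg/day row label is a plain unit slip.

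The conclusion rests only on figures printed in the protocol, with no outside assumption. The multiples measure the inconsistency. They are not evidence of harm or of bias in the triglyceride outcome. How many patients are affected depends on who is enrolled and whether anyone is titrated above 10 mg, which the protocol does not tell us. Which maximum was intended cannot be established from the text.

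**What to change.** 1. Choose one maximum daily dose. That decision belongs to the sponsor; the single-site volume and vial content above are relevant to it.
2. State that maximum identically in both section 2.2 paragraphs, in section 3.3 and in Protocol Table 1.
3. In Table 1, relabel the dose row mg/day and replace the 5.0 to 10.0 range with a reference to the section 3.3 dosing table, up to the stated maximum.

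The cost is amendment wording. No extra patients, visits or assays are needed.

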## 2.2 INCLUSION AND EXCLUSION CRITERIA

### *Inclusion criteria for initial phase of the study:*

- Previously completed study protocol:
  - CLINICAL PROTOCOL to investigate the efficacy of recombinant human leptin (METRELEPTIN) in nonalcoholic steatohepatitis (NASH) or nonalcoholic fatty liver disease (NAFLD) associated with lipodystrophy, MB002-014 (IRMBED: HUM00058708)
- Demonstrates clinical benefit as defined by meeting at least one of the following criteria upon completion of the above stated protocols:
  - Reduction of HbA1c  $\geq$  1.0% or,
  - Reduction of triglycerides  $\geq$  30% of baseline or,
  - Decrease in insulin requirements  $\geq$  40% or,
  - Reduction in total NASH score by  $\geq$  2 points,
  - Significant worsening of metabolic parameters after discontinuation of Metreleptin if discontinuation has been undertaken.
  - A health condition that appears to have significantly improved by metreleptin for which two independent health care providers make a request to prevent drug discontinuation. In addition, the PI has to document absence of contraindications for drug continuation (such as bone marrow suppression).
- Is male or female  $\geq$  5 years old at baseline.
- Is male, female not of childbearing potential, or meets all the following criteria if female of childbearing potential (including perimenopausal women who have had a menstrual period within one year):
  - Not breastfeeding
  - Negative pregnancy test result (human chorionic gonadotropin, beta subunit [ $\beta$ hCG]) at baseline (not applicable to hysterectomized females).
  - Must practice and be willing to continue to practice appropriate birth control (defined as a method which results in a low failure rate when use consistently and correctly, such as implants, injectables, oral contraceptives, some intrauterine contraceptive devices, sexual abstinence, tubal ligation, or a vasectomized partner) during the entire duration of metreleptin treatment.
- Has physician-confirmed lipodystrophy as defined by evidence of partial (limbs) loss of body fat outside the range of normal variation.
- If  $\geq$  18 years of age, is able to read, understand and sign the U of M IRBMED approved informed consent form (ICF), communicate with study physician and study team, understand and comply with protocol requirements.

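### The protocol gives two different maximum daily doses (10 mg and 15 mg), and its schedule row of 5.0 to 10.0 mg/day conflicts with its own dosing table

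*Protocol*

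**What the plan says.** Four places in the protocol set the dose.

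- **Section 2.2, Restorative leptin therapy.** The starting doses are flat by sex: "patients will be treated with 2.5 and 5 mg /day (male and female respectively". The maximum follows: "Higher dose titrations can be used in the judgment of the PI as indicated up to 10 mg daily". The paragraph expects doses to stay mostly unchanged, because patients arrive on a dose already found effective.
- **Section 2.2, Treatment.** "Dose may be titrated up to 15 mg daily based on metabolic response as needed". No weight condition is attached.
- **Section 3.3, dosing table.** The recommended daily dose is 0.06 mg/kg for either sex at 40 kg or less, 2.5 mg for men above 40 kg and 5.0 mg for women above 40 kg. The investigator may adjust the dose on clinical response. The only numeric limit in this section is on volume: "Injections at a single site will have a maximum allowable volume of 2.0 ml".
- **Appendix, Protocol Table 1.** The row whose label begins "Leptin (mg/kg/day" lists "5.0 – 10.0 mg/day" in all three visit columns, with no condition on sex or weight.

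The inclusion criteria admit patients who are at least "5 years old at baseline" and set no minimum weight.

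**The concern.** Dose limits are operative rules. Staff who dispense drug, the independent Study Monitor and an auditor should all read the same limit. Here a dose above 10 mg and up to 15 mg is outside one paragraph and inside the next, so it is undefined whether such a dose departs from the protocol. Section 3.3 does not settle this: it refers back to the doses given earlier and adds no daily maximum.

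The schedule row is a separate conflict. It applies from baseline, before any titration, and its lower end is above the recommended dose for two of the three groups in the Section 3.3 table. Its label and its entries are also in different units.

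A further gap is that the protocol gives patients of 40 kg or less a per-kg dose but no per-kg maximum. What is at stake is clear and safe dosing. The triglyceride and HbA1c outcomes are not touched.

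**Working it through.** The protocol states no derived figure to reproduce. The check compares its doses with one another.

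**Inputs.** Maxima of 10 mg and 15 mg (Section 2.2). Recommended doses of 0.06 mg/kg, 2.5 mg and 5.0 mg (Section 3.3). Schedule range of 5.0 to 10.0 mg/day (Appendix).

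**Step 1, the two maxima.** 15 − 10 = 5 mg; 15/10 = 1.5. The upper end of the schedule row agrees with the 10 mg maximum and so disagrees with the 15 mg one.

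**Step 2, schedule floor against the dosing table.** Multiple = 5.0 mg / recommended dose.

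| Group | Recommended dose | 5.0 mg as a multiple |
|---|---|---|
| Women above 40 kg | 5.0 mg | 5.0/5.0 = 1.0 |
| Men above 40 kg | 2.5 mg | 5.0/2.5 = 2.0 |
| 40 kg or less, either sex | at most 0.06 × 40 = 2.4 mg | at least 5.0/2.4 = 2.08 |

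The row fits only women above 40 kg. In the lowest band the multiple is 5.0/(0.06 × weight), which rises as weight falls, so 2.08 is its minimum and no patient weight has to be assumed.

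**Step 3, units.** The label is per kilogram and the entries are per day. The entries carry their own unit, so this is a labelling slip. It still has to be corrected, because the row also covers patients who are dosed per kilogram.

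**Step 4, the maxima against weight (secondary point).** Multiple = maximum / recommended dose.

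| Group | 10 mg maximum | 15 mg maximum |
|---|---|---|
| Women above 40 kg | 10/5.0 = 2.0 | 15/5.0 = 3.0 |
| Men above 40 kg | 10/2.5 = 4.0 | 15/2.5 = 6.0 |
| 40 kg or less | at least 10/2.4 = 4.17 | at least 15/2.4 = 6.25 |

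At 40 kg the multiples are close to those for men just above 40 kg (6.25 against 6.0) and about twice those for women. They grow as weight falls. At an assumed 20 kg the recommended dose is 0.06 × 20 = 1.2 mg, and the multiples are 10/1.2 = 8.3 and 15/1.2 = 12.5.

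**The case against.** The best defence is that little of this would be felt in practice. Enrolment is limited to at most 15 completers of the parent study, already on an effective dose that is expected to stay the same, and Section 3.3 lets the starting dose follow the dose at the end of the earlier studies. Leptin, weight and tolerability are checked at the six-monthly visits. Overdose is handled as a serious adverse event, and the Study Monitor can stop treatment in a patient. On this view the schedule row is a summary with a visible unit slip. Most of this stands, and it keeps the weight of the point modest. None of it says which maximum applies or makes the row agree with the table. The overdose definition in Section 5.10 contains no number, and the 2.0 mL limit is per injection site.

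The weight-related part needs more restraint. A reader might infer that small children can be given more than six times a permitted maximum of 2.4 mg. The documents do not support that:

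- The 0.06 mg/kg figure is a recommendation that the investigator may adjust, so a higher maximum does not contradict it.
- At 40 kg the multiple hardly differs from that for men above 40 kg.
- No eligible completer of 40 kg or less is shown. Section 6 mentions four pediatric patients across the parent study and another study, without weights. Section 3.4 says that little drug remains in the vials, whereas a dose of 2.4 mg from an 11.3 mg vial would leave 11.3 − 2.4 = 8.9 mg. That suggests, without proving it, that the patients described are not on low doses.
- Section 4.2 reports no dose relationship for the obesity-study and Brochure events it lists, although hypoglycemia is discussed in a separate paragraph.

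A reader might also take the range in "this goal can be achieved by administration of 0.02 to 0.10 mg/kg/day in adult males" as a limit. It is stated for adult males only, and the protocol's own 5.0 mg female dose exceeds 0.10 mg/kg below 5.0/0.10 = 50 kg.

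**Conclusion.** The dosing rules contradict each other and should be corrected. Two conflicts are firm and need no assumption about who enrols: the maximum is 10 mg in one paragraph and 15 mg in the next, and the schedule row excludes the 2.5 mg male dose under a label in the wrong unit. The row's 5.0 mg floor is also at least 2.1 times the recommendation for any patient of 40 kg or less.

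The lack of a weight-scaled maximum is a secondary gap. It rests on children from age 5 being eligible with no weight floor, and it has practical effect only if a completer of 40 kg or less enrols, which the documents leave open. The importance is modest, because the soft safeguards are real and no efficacy outcome is affected. The correction is still worth making: these are operative dosing rules, and putting them right costs almost nothing.

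**What to change.** 1. State one maximum daily dose, the same in the Restorative leptin therapy and Treatment paragraphs of Section 2.2.
2. Replace the dose row of Protocol Table 1 with a reference to the Section 3.3 dosing table. This removes the 5.0 mg floor and the unit mismatch together.
3. Secondary: say that the flat maximum applies above 40 kg, and have the sponsor set a mg/kg maximum beside the 0.06 mg/kg row for patients of 40 kg or less. The value has to come from the sponsor, since the documents support no particular figure.

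The cost is protocol wording only, with no added procedures or patients. The downside is slightly less dosing freedom for the investigator.
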